 - b. Persistence Hypothesis: DCS improvement of delusions compared to placebo will persist at 3 and 6 month follow-up as defined as maintenance of a 20% or greater reduction in the PSYRATS Delusions Subscale total score from baseline.

Tertiary

3. Identify mediators of delusional response to DCS.
 - a. Memory Consolidation Hypothesis: Change in 7-day thematic recall on the Logical Memory Test after the first dose of DCS will predict improvement on the PSYRATS Delusions Subscale total score at 12 weeks.
 - b. Cognitive Flexibility Hypothesis: Change in the number of alternative beliefs generated during the first compared to the second administration of the Alternative Beliefs exercise in the DCS group will predict improvement of the PSYRATS Delusions Subscale total score at 12 weeks.
4. Identify neural differences in patients compared to age-matched healthy control population.
 - a. Network connectivity hypothesis: Decreased connectivity between the hippocampus and prefrontal cortex in patients at rest and during encoding of stories

Study #:S12-02991

and images, DCS enhancement of connectivity.

b. Memory Hypothesis: Patient impairment of network connectivity will predict performance on immediate and 1-week delay memory relative to healthy controls

Background Significance:

Public Health Significance: Delusions remain a serious public health problem, with persistent antipsychotic-resistant delusions present in approximately 30% of schizophrenia patients. In addition, most patients experience intermittent psychotic relapse associated with major disruptions in rehabilitation and recovery. Persecutory delusions are associated with great psychological distress to patients and family members, whereas other forms of delusions commonly result in social and vocational disability, incarceration, and can result in harm to self or others.

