The SAPS will be performed at screening and four weeks later at baseline to identify subjects with persistence of sufficient delusional severity to enter the study. The clinical assessment battery will be comprised of the Psychotic Symptom Rating Scale (PSYRATS), Brief Psychiatric Rating Scale (BPRS), Scale for Assessment of Negative Symptoms (SANS), Calgary Depression Scale for Schizophrenia (CDSS), Clinical Global Impression (CGI) and Heinrich's Quality of Life Scale (QLS). We are using this broad battery of tests to compare treatment groups at baseline and to allow exploratory analyses to help us understand the effects of DCS on our primary outcomes and to guide selection of outcome measures for future studies. The clinical battery will be administered at baseline and weeks 4, 8, 12, 24, and, in most subjects,

Study #:S12-02991

36. In addition, the Delusion Subscale of the PSYRATS will be administered at weeks 2, 3, 6 & 10 to assess the time course of DCS effects on delusions. Ratings will be performed prior to the DCS/CBT session each week. Additionally, the Drug and Alcohol Questionnaire and the Pittsburgh Sleep Quality Index will be performed at baseline. Assessment of cognitive functioning will be measured by the MATRICS battery at baseline only since we have found no effect of daily or weekly DCS administration on this and similar cognitive batteries in four randomized controlled trials. The SAFTEE will be administered at weeks 3, 4, 8, and 12. The SAFTEE is a self-report measure on which the participant rates the severity of 55 side effects on a 4 point Likert Type scale. The scale also asks the participant to furnish an overall rating on the severity of all side effects. Participants will be followed regardless of whether they remain on study drug or comply with CBT sessions to permit an unbiased causal estimate of D-cycloserine treatment efficacy under the intention-to-treat principle. Additionally, a per protocol analysis will be performed using data only from subjects who have substantially complied with the protocol.

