Healthy subjects will be consented and screened for eligibility. Then, participants will perform a logical memory test, immediate recall test, and 25 minute recall. Participants will also perform a verbal fluency test. KVLT-R and BVMT-R and Rey Complex Figure test (RCFT).

Visit 2

Healthy subjects will perform the 1 week retrieval for the logical memory task, be given instructions for the scan test, and undergo the first set of MRI and fMRI scans.

Visit 3

Healthy subjects will complete the second set of MRI and fMRI scans.

Visit 4

Subjects will perform a memory recall task from the fMRI scan on visit 3 and a story segmentation task based on the fMRI scan on visit 2..

Data Analysis and Data Monitoring

Analysis Plan:

Primary: Between treatment differences in PSYRATS Delusions Subscale

Mean effects in week 12. The mean effect of DCS + CBT compared to Placebo + CBT on delusions will be tested using a linear mixed model repeated measures (MMRM) analysis of modified PSYRATS with fixed terms for study visit, DCS/Placebo treatment group and visit by treatment interaction. The model will include random subject effects. Baseline PSYRATS will be included in the model together with a baseline by treatment interaction term. The MMRM will assume a means model, an unstructured covariance matrix and parameter estimation will be based on restricted maximum likelihood. Because of the potential for failure of model convergence due to the requirement of a large number of interaction terms, only a few other covariates will be considered. These may include baseline SANS total score and demographic variables including age and gender, which may be predictive of outcome. To test treatment difference in change from baseline in PSYRATS, we will use a-pairwise contrast on the terms for DCS treatment by visit interaction. To examine differential treatment effects at each CBT week if there is significant interaction, we will perform tests of simple main effects. A significantly larger 12-week decline in mean PSYRATS total score for subjects receiving DSC supports the

Study #:S12-02991

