effectiveness of DCS. The probability of a type one error, the size of the test, will be controlled at 0.05, and all tests will be two-tailed. Overall alpha will be maintained at 0.05 for analyses of primary parameters. No adjustments will be made for multiplicity among secondary parameters analyzed. *Missing data*: The analysis will utilize the intention-to-treat principle. All randomized subjects, both completers and non-completers, will be included in the analysis without imputation. Estimates will be unbiased if follow-up data that are missing are "missing at random" conditional on the observed data and model assumptions.

Secondary: Characterizing onset and duration of effectiveness of DCS

a and b. Testing equality of the distributions of onset and duration. Onset is defined as the first week at which the criterion for response is met that lasts at least to the final week of the treatment period. Kaplan-Meier estimates of the survival distributions of time to onset of response will be obtained and the survival distributions will be compared using the log-rank test. The survival distribution, $H(t)$, is the probability that onset will occur after time t . Duration is defined as the number of weeks from onset to offset. Offset for a responder is the first week at which the criterion for response is no longer met. The treatment specific survival distributions of duration will similarly be compared using the log-rank test. The null hypothesis for the second primary outcome measure is that there is no difference between the two treatment groups in the proportion of subjects who are responders (defined as a 20% or greater reduction in PSYRATS Delusions Subscale total score) beginning in week two to the end of the treatment phase. The statistical analysis will be based on a repeated measures logistic regression model. The independent terms in the model will include the same variables and covariates used in the MMRM analysis. By the definition of responder, there cannot be any missing data.

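### Hypothesis 2b (DCS versus placebo at 3 and 6 months) has no named all-randomized contrast at week 24 or 36, and the duration log-rank test assigned to it does not answer the question

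*Combined protocol and SAP*

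**What the plan says.** The Specific Aims state that "DCS improvement of delusions compared to placebo will persist at 3 and 6 month follow-up", with persistence defined as "maintenance of a 20% or greater reduction in the PSYRATS Delusions Subscale total score from baseline". The hypothesis therefore has a comparator, two time points and a binary endpoint.

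Assessments schedules the ratings: "The clinical battery will be administered at baseline and weeks 4, 8, 12, 24, and, in most subjects", week 36. Counted from the end of treatment at week 12, weeks 24 and 36 are the 3- and 6-month visits. The same section commits to intention-to-treat follow-up: "Participants will be followed regardless of whether they remain on study drug or comply with CBT sessions".

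The Analysis Plan then provides the following:

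- **Primary (MMRM).** The paragraph is titled for week 12. Its further visit-level tests are limited to treatment: "To examine differential treatment effects at each CBT week if there is significant interaction, we will perform tests of simple main effects". The visits in the model are not listed.
- **Secondary, a and b.** The rule for onset reads: "Onset is defined as the first week at which the criterion for response is met that lasts at least to the final week". The week meant is the last one on treatment. For duration the plan says: "Duration is defined as the number of weeks from onset to offset". Offset is defined for responders. The comparison is then given as: "The treatment specific survival distributions of duration will similarly be compared using the log-rank test". Risk set and censoring are not given.
- **Secondary, responder proportion.** A repeated measures logistic model covers week two to the end of the treatment phase.
- **Secondary, c (cure model).** This concerns onset and the probability of response by the end of treatment.

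No power or sample size is given for week 24 or 36.

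**The concern.** The hypothesis asks whether more DCS than placebo subjects are still improved at two fixed visits. The test assigned to it asks how long response lasted from its start, in a group the plan does not define. A null result from a small responder subgroup would say little about persistence. A positive result could reflect earlier onset, or more response by week 12, rather than better maintenance. With risk set, censoring and missing-data rule unstated, the analyst would have to choose them later, and the choice could decide the result. Persistence is one of two secondary hypotheses; the week 12 primary conclusion does not depend on it.

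**Working it through.** **1. The plan's own figures.** Inputs from Estimation of statistical power: 60 evaluable subjects, 1:1, so 30 per arm; effect size 0.8; response 10% versus 50%. Two-sided alpha is 0.05.

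- Means: 0.8 × √(30/2) − 1.96 = 3.098 − 1.96 = 1.138, power 87.3% (86.1% with the t distribution). The stated figure of more than 85% reproduces.
- Proportions, unpooled: 0.40 / √((0.09 + 0.25)/30) − 1.96 = 3.757 − 1.96 = 1.797, power 96.4% (94.3% with pooled variance). The stated figure of more than 95% reproduces to within about a point.

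The first concerns week 12. The second has no time point. Neither covers follow-up.

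**2. Duration test, responders only (the natural reading).** A subject without onset has no duration, and offset is defined for responders.

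- *Selection.* If 10% and 50% were sustained-response rates (an assumption), 30 × 0.10 = 3 placebo and 30 × 0.50 = 15 DCS subjects would enter. The chance of at most one placebo responder is 0.9^30 + 30 × 0.1 × 0.9^29 = 0.042 + 0.141 = 0.18. At a 5% placebo rate it is 0.55.
- *Onset mixed with persistence.* Take two responders, both first seen without response at week 24. Onset at week 4 gives 24 − 4 = 20 weeks. Onset at week 12 gives 24 − 12 = 12 weeks. Their status at 3 months is identical, but their scores differ by 8 weeks.
- *Coarse observation.* Onset requires response to the end of treatment, so offset can be seen only at week 24 or 36.

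**3. Duration test, non-responders at zero (less natural, but not excluded).** At 10% and 50%, 27 placebo and 15 DCS subjects have an event at time zero. That step alone gives observed minus expected placebo events of 27 − 42 × 30/60 = 6, with variance 42 × 18 × 30 × 30 / (60² × 59) = 3.20, so z = 6/1.79 = 3.35 before any follow-up rating is used. In simulation (5,000 trials), the whole test favours DCS in about 82% of trials even if every responder in both arms has lost response by week 24, when 2b is false.

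**4. All-randomized comparison at one follow-up visit.** Assume 30 per arm, the 10% and 50% rates, equal maintenance in both arms and complete data. Power by exact enumeration:

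| Assumed maintenance | Placebo vs DCS still improved | Pearson | Fisher |
|---|---|---|---|
| 80% | 8% vs 40% | 86% | 79% |
| 50% | 5% vs 25% | 63% | 44% |
| 25% | 2.5% vs 12.5% | 31% | 9% |

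Pearson's true size reaches 5.5% with 30 per arm and 6.0% with 32, above the 0.05 the plan says it will control. Fisher does not exceed 0.05.

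**5. Counting unobserved ratings as not improved.** Suppose 40% in each arm are truly improved, with 40% of placebo and 10% of DCS ratings missing (assumed). Apparent rates are 0.40 × 0.60 = 24% and 0.40 × 0.90 = 36%. Pearson then rejects in 17% of trials although there is no difference.

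**The case against.** **The MMRM may already cover follow-up.** It has visit and visit-by-treatment terms and does not list its visits, so weeks 24 and 36 may be in it. This stands. A reader might infer that the log-rank test is the only analysis able to use data after week 12; the documents do not establish that. What is missing is a named contrast at those weeks, and the 2b endpoint is binary, not a mean.

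**2b does have a test.** The item labelled a and b matches hypotheses 2a and 2b and compares duration by arm, and maintenance can be read as conditional on response. This also stands: it would be wrong to say that 2b was left without any analysis, and duration among responders deserves to be kept. But the hypothesis says compared to placebo, and follow-up is intention-to-treat, so an all-randomized comparison is needed too.

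**Low power of the duration test cannot be quantified.** A reader might take the 3 versus 15 split and attach a log-rank power to it. The documents give no hazard ratio. Exponential durations with every subject losing response would contradict an onset rule that guarantees response to the end of treatment, and would ignore that later offset is seen at only two visits. No such figure is relied on here.

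**The replacement is not pure persistence either.** With equal maintenance in both arms, its power comes from the difference in response during treatment, and a first response at week 24 would count. That is correct. It nevertheless tests what 2b states: whether an advantage over placebo is present at those visits.

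**Conclusion.** The plan should be changed on this point. Hypothesis 2b is a between-arm claim at two visits whose ratings are scheduled, and no all-randomized contrast is named at either. The duration log-rank test answers a different question on either reading of its risk set.

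The 20-versus-12-week example follows from the plan's definitions alone. The 3-versus-15 split and the 18% chance assume that the 10% and 50% planning rates describe sustained response, which the plan does not say. The 82% figure needs the less natural reading and complete relapse in both arms, so it is an illustration, not a forecast.

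A reader might go on to infer that the trial's efficacy conclusion is compromised. It is not: this concerns a secondary aim of a proof-of-concept trial, and the primary week 12 comparison is unaffected.

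**What to change.** Rewrite the persistence paragraph as follows.

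1. **Test of 2b.** In all randomized subjects, compare the arms on the proportion with a 20% or greater PSYRATS Delusions reduction from baseline, at week 24 and at week 36. Name a test that holds the stated 0.05 size, for example an exact test. Say whether the claim needs both visits; a week 24-then-36 gate is optional.
2. **Missing ratings.** Use the missing-at-random basis the plan already states. One route is a likelihood fit of its repeated measures logistic model extended to both visits, with its p-value obtained by re-randomization or another method that holds size. That model needs a stated fallback for when no placebo subject is still improved: at week 24 with complete data, the chance is 0.92^30 = 8%, 0.95^30 = 21% or 0.975^30 = 47% at 80%, 50% or 25% maintenance. Report counting unobserved ratings as not improved as a sensitivity analysis.
3. **Support.** Report MMRM mean contrasts at weeks 24 and 36.
4. **Week 36.** State which subjects are not scheduled for it.
5. **Duration.** Keep it as supportive among responders, with risk set and censoring stated and time counted from week 12, so that earlier onset is not scored as longer persistence.

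Cost: one rewritten paragraph, using ratings already scheduled. Power is limited if maintenance is low, more so with an exact test (Fisher 79%, 44% and 9% at 80%, 50% and 25% maintenance), and missing ratings will lower it further. The result must be reported as reflecting both response during treatment and its maintenance.

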CBT/DCS Protocol: Individual manualized CBT sessions will last 50 minutes and will be offered weekly for 12 weeks. The first two sessions will focus on engagement, characterization of delusions, and formulation of a treatment plan. Sessions 3 & 4 will consist of an alternative beliefs exercise as employed in our pilot trial in which subjects are trained to produce as many explanations as possible for a series of benign social vignettes (e.g., a taxi driver is staring at you), culminating with their own delusional belief (32). The exercise is structured with a fixed set of vignettes which allows us to record the number of alternative explanations generated by the subject during the exercise as a measure of cognitive flexibility. The remaining 8 sessions will include exploration of antecedents of delusional beliefs, development of a normalizing rationale, cognitive restructuring, testing of explanatory models, and review and consolidation. Study drug (DCS 50 mg or matching placebo) will be administered orally, 1 hour prior to sessions 3-12. Placebo will be administered prior to sessions 1 & 2. DCS and matching placebo capsules will be formulated by the NYUMC research pharmacy.

If a subject misses three consecutive study visits and corresponding CBT sessions, he/she will be withdrawn from the study. These missed visits and sessions may compromise the integrity of the study data and adversely affect the therapeutic alliance which is important in the CBT treatment.

CBT will be provided by [name], a PhD psychologist who trained under [name] at MGH using manualized CBT protocols. A second PhD level therapist may be added and will have at least one year of intensive CBT training and experience working with psychosis. To ensure that there will be no effect due to CBT therapist, balance will be maintained such that each therapist will be assigned to the same number of subjects assigned to DCS as to placebo. This will be accomplished by a statistician independent of the study. Before initiation of the study, training will be provided by [name] who will also provide weekly supervision by video-

Study #:S12-02991

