conference and will monitor treatment fidelity by evaluating audiotapes from 20% of sessions using the Cognitive Therapy for Psychosis Adherence Scale (CTPAS) (34). [name] recently participated in the development of the CBT protocol and conducted trainings for the NIMH-funded RAISE Study. Competency will be defined as a score of at least 10 on the CTPAS. Competency must be achieved by each study therapist with a pilot case prior to participation in the study and must be maintained throughout the study. Additional training will be provided if CTPAS scores drop below 10.

Rationale for DCS/CBT protocol design: The design of our protocol for combining DCS with CBT follows from several findings: 1.) DCS effects may decrease over time with repeated dosing (21) although we believe that once-weekly dosing reduces the risk of tachyphylaxis, 2.) DCS is effective for novel learning only (22) and 3.) we previously found large effects when DCS was combined with the first of two sessions of an alternative beliefs exercise which was designed to exploit DCS effects on memory consolidation and cognitive flexibility (32). Therefore, we will begin with two introductory sessions unaccompanied by study drug; study drug will first be administered with an alternative beliefs exercise at session #3. We will then continue weekly study drug administration one hour prior to CBT sessions and will follow session #3 with a second session of the alternative beliefs exercise in order to replicate the intervention provided in our pilot trial (two consecutive sessions of an alternative beliefs exercise) since delusions continued to improve following the second exposure to the exercise. The remaining 8 sessions will consist of standard CBT approaches to delusions to consolidate therapeutic effects.

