We selected a 12 session CBT protocol to ensure an adequate CBT intervention in the placebo group consistent with clinical practice. Because our treatment is focused on delusions and their behavioral consequences, 12 sessions are adequate whereas longer treatment, such as the 16 session protocol that we developed for our CBT monotherapy trial, may be necessary for treatments that address the full range of schizophrenia symptoms. In support of a brief treatment, Turkington, Kingdon and colleagues (9) developed a 6-session CBT protocol which demonstrated efficacy compared to treatment as usual in a sample of 442 schizophrenia subjects (9). In studies of DCS augmentation of CBT for anxiety disorders, DCS efficacy compared to placebo was greatest in trials of short duration (2-5 weeks) compared to longer trials, possibly reflecting tachyphylaxis or a ceiling effect due to the efficacy of CBT administered alone for anxiety disorders (24). Because of the relatively small effect of CBT for delusions we do not expect to encounter a ceiling effect. Subjects will receive 10 weekly doses of DCS in our proposed trial and we will track the response of delusions over this time frame. In our 8 week study of DCS facilitation of cognitive remediation, enhancement of learning plateaued between weeks 4-8; we anticipate a similar pattern with DCS facilitation of CBT. Our previous manualized CBT protocols were developed by [name] based on manuals and casebooks produced by Tarrington and Kingdon (35). [name] and [name] will develop a manualized CBT protocol based on these resources with consultation from [name]. Other texts such as those produced by Fowler and colleagues (36) Chadwick and colleagues (37) and Nelson (38) will also be used.

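### The secondary responder comparison opens in week two; read as study week 2, that rating precedes any DCS, so the window should be tied to the first DCS dose

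*Combined protocol and SAP*

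**What the plan says.** **Window and model.** The Analysis Plan (Secondary, parts a and b) sets the responder null as equality of the "proportion of subjects who are responders (defined as a 20% or greater reduction in PSYRATS Delusions Subscale total score) beginning in week two" and running to the end of treatment. It uses repeated measures logistic regression with the same terms as the primary MMRM, which include visit by treatment.

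**Hypothesis 2a.** Specific Aims places this hypothesis two weeks into DCS treatment, with response defined as a 20% reduction.

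**Drug timing.** CBT/DCS Protocol states: "Placebo will be administered prior to sessions 1 & 2", and "Study drug (DCS 50 mg or matching placebo) will be administered orally, 1 hour prior to sessions 3-12". The design rationale agrees: "study drug will first be administered with an alternative beliefs exercise at session #3".

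**Rating timing.** Under Assessments, "The clinical battery will be administered at baseline and weeks 4, 8, 12, 24" and, for most subjects, 36; in addition "the Delusion Subscale of the PSYRATS will be administered at weeks 2, 3, 6 & 10". The order within a week is also given: "Ratings will be performed prior to the DCS/CBT session each week". The rated treatment visits are therefore weeks 2, 3, 4, 6, 8, 10 and 12.

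**Week labels for the first dose.** Assessment of memory consolidation puts the first study-drug dose and story B at week 3. Estimation of statistical power calls the week 3 assessment the first one after study drug and uses it to define evaluable subjects. Assessment of cognitive flexibility lists the exercise at weeks 3, 4 and 12, then says it is first given at week 4, then treats a week 2 administration as the baseline value.

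**The concern.** Study week 2 is a scheduled PSYRATS visit, so a programmer following the text literally could include it as a responder outcome visit. That rating cannot show a drug effect. A visit-averaged responder difference would then be pulled toward zero. If response had to be sustained from that visit onward, subjects would need to respond before receiving any DCS.

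The plan does not say whether week two counts from study start or from the first DCS dose. It also leaves open whether 2a is a comparison over a window or at one visit, and whether response is judged per visit or must be sustained. The conflicting week labels mean the sections cannot settle this between them.

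**Working it through.** **1. The plan's own responder power.** Inputs from Estimation of statistical power and the Analysis Plan: 60 evaluable, 1:1 (30 per arm), 10% vs 50%, two-sided 0.05, stated power above 95%.

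- Pooled: the null SE is √(2 × 0.30 × 0.70 / 30) = 0.118 and the alternative SE is √((0.09 + 0.25) / 30) = 0.106. Then z = (0.40 − 1.96 × 0.118) / 0.106 ≈ 1.58, which gives 94.3%.
- Unpooled: 0.40 / 0.106 − 1.96 ≈ 1.80, which gives 96.4%.

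The stated figure is reproduced closely enough and is not in dispute.

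**2. DCS doses received before each rating** (drug from session 3, rating before the session):

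| Rating week | 2 | 3 | 4 | 6 | 8 | 10 | 12 |
|---|---|---|---|---|---|---|---|
| Session k in week k | 0 | 0 | 1 | 3 | 5 | 7 | 9 |
| Session 1 in week 0 | 0 | 1 | 2 | 4 | 6 | 8 | 10 |

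The first row fits the memory consolidation text. The second fits the power text, where week 3 is post-drug. Week 2 is zero in both. A first exercise at week 4, one of the labels in the cognitive flexibility text, would put session 12 in week 13. That is outside the 12-week course, so I did not carry it forward.

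**3. Where 2a falls.** Two weeks after the first dose is week 4 if session 1 is at week 0 (first dose week 2). It is week 5 if session k is at week k (first dose week 3). Week 5 has no rating.

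**4. Size of the dilution on the study-week reading.** With k pre-dose visits among seven equally weighted visits, the averaged difference is Δ × (7 − k) / 7. Taking the plan's rates as per-visit rates, Δ = 40 points:

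- k = 1: 40 × 6/7 = 34 points
- k = 2: 40 × 5/7 = 29 points

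The shrinkage fraction does not depend on how the effect develops after dosing.

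**5. Power cost.** This is a simulation with 10,000 trials per setting (20,000 for slow build-up), exchangeable latent-normal visits, and a Welch test on each subject's mean responder proportion. The Welch test stands in for a visit-averaged contrast from the logistic model. There are 30 subjects per arm. Each cell gives power with all seven visits vs post-dose visits only.

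| Setting | One pre-dose visit | Two pre-dose visits |
|---|---|---|
| 10% vs 50%, correlation 0.6 | 99.8% vs >99.9% | 98.9% vs 99.9% |
| 10% vs 50%, correlation 0.8 | 98.4% vs 99.4% | 95.7% vs 99.4% |
| Build-up over 4 weeks to 50%, correlation 0.6 | 97.2% vs 98.9% | 92.8% vs 98.6% |
| 10% vs 31.5%, correlation 0.6 | 79.5% vs 86.4% | 67.6% vs 85.0% |

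The correlations are assumptions. The 31.5% rate is also assumed, from a 0.8 SD latent shift: Φ(−1.28 + 0.8) = Φ(−0.48) ≈ 0.315. The build-up row is an assumption suggested by the remark that "enhancement of learning plateaued between weeks 4-8; we anticipate a similar pattern with DCS facilitation of CBT".

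**6. Other readings.**

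- *Visit-specific contrast at a post-dose visit:* no dilution.
- *Onset at any time in the window:* the plan requires onset to last to the final week, so a subject has onset exactly when responding at the final week. Where the window opens makes no difference.
- *Response sustained from study week 2:* the DCS rate cannot exceed the response rate at week 2, before any DCS. If that were the 10% assumed for placebo, 10% would be the ceiling, against the planned 50%.

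**The case against.** The strongest reply is that week two means week two of DCS. The responder null would then come close to restating 2a as a window from two weeks of DCS onward, with a named model and a treatment term. This is a plausible reading and it removes the pre-dose problem. It is not stated, however, and the primary analysis section counts in CBT weeks.

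A reader might infer that 2a has no test at all. The documents do not support that. On the DCS-week reading there is a windowed test. The primary section also has an unconditional pairwise treatment-by-visit contrast; only its simple main effects wait for a significant interaction. Both are written for mean PSYRATS, but the responder model carries the same terms, so a visit-level contrast is a short step away.

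A reader might also infer a serious loss of power. The losses of 7 and 17 points in the last row need three things together: the study-week reading, equal-weight averaging (which the plan does not state) and a 31.5% response rate that the documents do not contain. Collapsing the averaged rates into one two-proportion test gives 94%, 87% and 74% for zero, one and two pre-dose visits. That treats a seven-visit average as though it were a single binary rating.

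The sustained-response reading gives one outcome per subject and fits poorly with a repeated measures model. Finally, the text calls this comparison a second primary outcome, but it sits under the Secondary heading and Aim 2 is secondary. That label is a separate matter and does not raise the stakes here.

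**Conclusion.** The concern holds in a limited form. Taken literally as study weeks, the stated window puts one or two pre-dose ratings among the seven responder outcome visits. One of them, week 2, is pre-dose on either numbering. A visit-averaged difference would shrink by 1/7 or 2/7. At the planned rates, with an assumed correlation of 0.6, power falls by about one point or less. At correlation 0.8 it still stays above 95%. The cost grows if the effect is smaller or builds slowly, and it is nil for post-dose visit-specific contrasts and for the DCS-week reading.

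Pre-dose visits add a true difference of zero, so type I error is not inflated. The week-12 comparison of PSYRATS means is untouched. Severity is minor: this is a secondary analysis and the repair is wording.

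**What to change.** 1. Reconcile the week and session numbering across Assessments, Assessment of memory consolidation, Assessment of cognitive flexibility and Estimation of statistical power. Include which rating is the first after study drug, because the evaluable definition depends on it.
2. Anchor the responder window to the first DCS dose. If the second week of DCS was meant, say so and keep that window. If study week was meant, start at the first post-dose rating (week 3 if session 1 is at week 0, week 4 if session k is at week k) and do not treat pre-dose ratings as outcome visits.
3. State whether response is per visit or sustained, and whether 2a is tested over the window or at one visit using the treatment-by-visit term already in the model. If one visit is chosen, use week 4 if session 1 is at week 0. If session k is at week k, use week 6 and restate 2a, since week 5 has no rating and week 6 follows three doses.
4. Keep the post-dose averaged comparison in either case.

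The cost is wording only, with no new ratings. Step 4 matters because one visit has less power. At 30 per arm, exact chi-square power is 94.9% at 10% vs 50% and 55.0% at 10% vs 31.5%, below even the diluted averages. Under the four-week build-up assumption, a single-visit 2a test has 37% power at week 4 (first dose week 2) or 73% at week 6 (first dose week 3).
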